### **10.1.6 End of Surveillance (Telephone Contact)**

The following procedures will be performed during the end of surveillance telephone contact (approximately 30 April 2018 (the duration of surveillance period may be adjusted, based on the observed epidemiology during the season in participating countries); acceptable interval of  $\pm$  3 days):

- Record updates on any change in the subject's health and report any SAEs or NOCDs;
- Record updates on any changes in concomitant medications used to treat conditions reported in the subject's medical history, AEs that started before Day 21 and were still ongoing after Day 21, SAEs, AEs leading to withdrawal from the study, or NOCDs as well as prohibited medication use (if any);
- Confirm that the subject has continued to comply with protocol requirements (e.g. no use of prohibited concomitant medications, use of an adequate contraceptive method, reporting of any respiratory illness or ILI symptoms).

Any subject who withdraws consent from the study will be asked to participate in the final telephone contact within two weeks of withdrawal, if the subject agrees.

## **10.2 Efficacy**

### **10.2.1 Efficacy Evaluations**

Following randomization and vaccination, subjects will be instructed to report respiratory symptoms and symptoms meeting the definition of ILI from Day 14 until the end of the surveillance period (passive surveillance). The subjects will be given a reminder aid listing the symptoms of respiratory illness and ILI and contact information for the study site. During this same period, active surveillance will also be performed: respiratory illness symptoms will be solicited a minimum of three times per week. At least one of these contacts each week will be through a scripted telephone call, with the remaining contacts via text messaging; a higher

---

proportion of telephone contacts may be used if deemed appropriate by the clinical site (e.g. difficulty in obtaining responses via text messaging).

A respiratory illness will be defined as the occurrence of a new onset of one or more of the following symptoms that persist(s) for or reoccur(s) after a period of at least 12 hours:

- Sneezing;
- Stuffy or runny nose (nasal congestion);
- Sore throat;
- Cough;
- Sputum production;
- Wheezing;
- Difficulty breathing.

An episode is considered to extend from the first day of the first symptom to the last day of the last symptom. As outlined in Section 10.1.4, in most instances a new episode can only begin after resolution of all symptoms of the previous episode, with a separation of a seven-day symptom-free interval between episodes.

Within 36 hours (preferably within 24 hours) after the reporting of a respiratory illness, the clinic site will collect nasopharyngeal (NP) swabs from the subject (two per subject per event). The swabs must be collected prior to the use of any influenza antiviral treatment medication (e.g. oseltamivir, zanamivir, rapivab). If the respiratory illness starts prior to Day 14, swabs are not to be collected, even if symptoms persist beyond Day 14. One swab will be submitted for analysis by multiplex RT-PCR. In the event of a positive RT-PCR result (positive for A or B strains), the second swab will be used to attempt to isolate the virus or for additional cell-culture testing (typing, subtyping, and strain identification and genetic sequencing using HI assay against a panel of known standard ferret reference antisera to different viral strains) to determine if the virus detected is matched or similar to any of the strains covered in the vaccine formulation for the respective season. A positive RT-PCR result will be considered a laboratory-confirmed case of influenza. Any respiratory illness must be followed up for 30 days following the start date; this follow up will be conducted via the planned active surveillance contacts (telephone and text messaging), using a script. At the end of the 30-day follow up, a questionnaire regarding disease burden due to the respiratory illness will be completed (Section 19.2); subjects will be provided with a memory aid (Section 19.3) for use over the 30 days, to facilitate accurate reporting at the end of the follow-up period.

ILI will also be monitored during this study. A subject will be considered to have protocol-defined ILI if the following two conditions are both met between Day 14 and the end of the surveillance period:

- He/she has at least one of the following pre-defined respiratory symptoms:
  - Sore throat;
  - Cough;

- Sputum production;
- Wheezing; or
- Difficulty breathing;

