## 4 STUDY DESIGN AND RATIONALE

### 4.1 Overview of Study Design

This randomized, observer-blind, placebo-controlled multicenter, Phase 3 study will be conducted at multiple sites. The composition of the Quadrivalent VLP Influenza Vaccine to be used in this study includes a mix of recombinant H1, H3, and two B hemagglutinin proteins expressed as VLPs for the 2017-2018 influenza virus strains (see Investigational Product Management Manual).

Approximately 10,000 healthy male and female subjects aged 18 to 64 years will be randomized in a 1:1 ratio into one of two parallel treatment groups, such that approximately 5,000 subjects will receive the Quadrivalent VLP Influenza Vaccine at a dose of 30 µg/strain and approximately 5,000 subjects will receive the placebo. Within the two treatment groups, subjects will be stratified by site and two age groups (18-49 years of age and 50-64 years of age in a 1:1 ratio).

A basic outline of the study design is presented in [Figure 1](#).

\* Subset of 400 subjects for CMI and humoral assessments

† August / September for North America and Europe; approximately early November for Asia

[figure not shown]
‡ The duration of the surveillance period may be adjusted, based on the observed epidemiology during the season.

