### **5.3 Prior and Concomitant Therapy**

Any new or changed medications reported by the subject post-vaccination and through to the end of the study will be recorded in the electronic case report form (eCRF) as a concomitant medication. Since AEs may be secondary to new medications, the Investigator will explore the reasons for the change or for the new medication intake and document these AEs, if any.

Concomitant medications must be reported in the eCRF (reason for use, dates of administration, dosage, and route) if the use meets the following conditions:

- Within 30 days preceding vaccination: any treatments and/or medications specifically contraindicated (e.g. influenza vaccines, any immunoglobulins or other blood products, or any immune modifying drugs, etc.);

- From randomization to Day 21, inclusive: any medication (including, but not limited to, over-the-counter medicines such as aspirin or antacids), vitamins, and mineral supplements;
- From Day 22 to the end of the study, inclusive: any concomitant medication(s) administered to treat a NOCD (see Section 13.1.4 for definition of NOCD), SAE, or AE leading to withdrawal; any concomitant medication used to treat an AE that occurred before Day 21 and that is still being used afterwards (i.e. on-going use); and any concomitant medications used to treat a protocol-defined respiratory illness or ILI;
- Any concomitant medication used to treat conditions reported as medical history;
- Any investigational medication or vaccine; any vaccine not foreseen in the study protocol.

Please refer to the eCRF completion guidelines for details of data entry requirements.

Given that an important objective of this study is to evaluate the tolerability of the study vaccine, the use of prophylactic medications to prevent or pre-empt symptoms due to vaccination is specifically prohibited up to Day 7 (end of collection of solicited symptoms). A prophylactic medication is a medication administered in the absence of ANY symptom and in anticipation of a reaction to the vaccination (e.g. an antipyretic is considered to be prophylactic when it is given in the absence of fever or any other symptoms, to prevent fever from occurring, vitamins used to boost immune system, etc.).

The use of influenza antiviral treatment (e.g. oseltamivir, zanamivir, rapivab) is not permitted until the NP swab is collected.

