#### **12.1.3 Per Protocol Set**

The PP set will consist of the subjects who participated in the study until at least the end of the peak period (approximately the end of February for Europe and North America) or for at least five months or until the end of the surveillance period (other countries); had no major protocol deviations related to subject eligibility, the ability to develop a valid immune response, prohibited medication use, or the efficacy analyses; and who received the vaccine or placebo. Major protocol deviations will be identified and documented during a blinded data review prior to database lock and confirmed at the time of database lock. The PP set will be the primary analysis population for the efficacy and immunogenicity endpoints. Subjects who received the wrong treatment, but for whom the treatment received can be unequivocally confirmed, will be analyzed as treated, provided they have no other deviations that compromise their data.

The analyses of all efficacy endpoints will be performed using the efficacy PP population and the FAS population.

The immunogenicity PP set will consist of the subset of subjects who participated in the immunogenicity portion of the study, who had a Day 21 immunogenicity sample collection; who had no major deviations related to subject eligibility, the ability to develop a valid immune response, prohibited medication use, or the immunogenicity analyses; and who received the vaccine or placebo. Subjects who received the wrong treatment, but for whom the treatment

---

received can be unequivocally confirmed, will be analyzed as treated, provided they have no other deviations that compromise their data.

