## **12.2 Sample Size Determination**

The sample size of approximately 10,000 subjects (5,000 subjects per treatment group) was selected based on the assumption that the Quadrivalent VLP Influenza Vaccine would have a VE of at least 70 % and that the ARU would be 2 % or greater for laboratory-confirmed influenza caused by vaccine-matched strains. The sample size was chosen to have 90 % power to determine whether the lower bound of the two-sided 95 % CI for the primary endpoint would be greater than 40 %, assuming a 10 % attrition rate.

If the ARU is lower than 2 %, but greater than or equal to 1.5 %, this sample size will have an 80 % power to determine whether the lower bound of the two-sided 95 % CI for the primary endpoint (VE) would be greater than 40 %, assuming a 10 % attrition rate.

A protocol amendment will be issued to address changes to the enrolment plan in the event of insufficient ARU.

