5 SAMPLE SIZE AND POWER

The sample size of approximately 10,000 subjects (5,000 subjects per treatment group) was selected based on the assumption that the Quadrivalent VLP Influenza Vaccine would have a VE of at least 70% and that the attack rate in unvaccinated subjects (ARU) would be 2% or greater for laboratory-confirmed influenza cases caused by vaccine-matched strains. The sample size was chosen to have 90% power to determine whether the lower bound (LB) of the two-sided 95% CI for the primary endpoint would be greater than 40%, assuming a 10% attrition rate.

If the ARU is lower than 2%, but greater than or equal to 1.5%, this sample size will have an 80% power to determine whether the LB of the two-sided 95% CI for the primary endpoint (VE) would be greater than 40%, assuming a 10% attrition rate.

A protocol amendment will be issued to address changes to the enrollment plan or to the study extension into another season to enrol more subjects in the event of insufficient ARU.

Table 3 shows the sample size simulations result. The simulation was repeated 1000 times in order to calculate the power.

Table 3 Sample Size Simulation Result

Placebo Control AR (ARU)	VE (vs placebo)	LB of 95% CI	Power	Sample Size per Group
2%	70%	40%	90%	4430
1.50%	70%	40%	80%	4490

[Note] Under the assumptions of 70% vaccine efficacy (VE) and 2% influenza attack rate (Placebo), we expect a total of 116 to 130 cases of influenza (89 cases for Placebo and 27 cases for VLP in case of 4430 per group considering 10% dropout rate, 100 cases for Placebo and 30 cases for 5000 per group).

If the influenza attack rate is lower than 2%, but greater than or equal to 1.5%, we expect a minimum of 89 total cases.

Immunogenicity Subset

A sample size of 300 subjects (for the VLP vaccine group) was selected to ensure that the LBs of the 95% CI for the co-primary endpoints (SC and SP rates) for each strain meet CBER's criteria with 80% power (individual power is 97.4%).

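### The swab-before-antiviral rule and the PP definition together can drop early-treated influenza cases: the cost is cases and power, with bias in VE only if the loss differs by arm

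*Protocol*

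**What the plan says.** **Order of swab and antiviral.** Protocol 10.2.1 states: "The swabs must be collected prior to the use of any influenza antiviral treatment medication". SAP 8.6.1 repeats this, and Table 2 note 1 and the notes to Figure 2 say the same in both documents. Protocol 5.3 adds that influenza antiviral treatment "is not permitted until the NP swab is collected". Section 5.4 points to exclusion criterion 17 (planned antiviral use before swabbing) as one of the prohibited therapies.

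**Who is swabbed.** Table 1 note 5, in both documents, calls for swabs from any subject with a respiratory illness from Day 14. The one exception it gives is illness starting before Day 14. The 36-hour window runs from the report of illness, not from its onset (Protocol 10.1.4).

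**Analysis sets.** PP subjects must have "had no major protocol deviations related to subject eligibility, the ability to develop a valid immune response, prohibited medication use, or the efficacy analyses" (Protocol 12.1.3; SAP 6.3 agrees). PP is primary for efficacy and FAS is the sensitivity analysis. Deviations are classified at a blinded review, and a subject is excluded only if the deviation is judged to affect the analyses (SAP 6.5). The FAS definition (SAP 6.2) has no medication condition.

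**What is a case.** A positive RT-PCR makes an illness laboratory-confirmed influenza. The primary endpoint also needs a vaccine-matched or antigenically similar strain, determined from the second swab. Un-typed cases enter only the any-strain endpoints.

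**The concern.** Because the window starts at reporting, a subject can be given an antiviral by an outside clinician before the site hears of the illness. The documents do not say whether the site should then swab, how a positive result from that swab is counted, or whether the deviation is major. A site following 10.2.1 literally may not swab; a site following Table 1 note 5 will. SAP 7.2 leaves missing efficacy measurements unreplaced and excludes the subject, but it is not clear whether that covers a swab that was never taken.

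There are two routes of loss:

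- An unswabbed illness has no RT-PCR result, so it cannot be a case in PP or in FAS.
- A swabbed, positive subject can be removed from PP for prohibited medication, and stays in FAS.

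In both routes, what decides the loss is treatment of the illness that the endpoint counts, so it happens after randomization and depends on the outcome. The success criterion rests on a modest number of cases, and a shortfall in cases can trigger an amendment to extend the study (Protocol 4.1 and 12.2).

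**Working it through.** **Inputs from the documents.** Protocol 12.2 assumes that the vaccine "would have a VE of at least 70 % and that the ARU would be 2 % or greater", so p0 = 0.02, RR = 0.30 and p1 = 0.006. Success means the "lower bound (LB) of the two-sided 95% CI for the primary endpoint would be greater than 40" per cent, that is, an upper limit for RR below 0.60. On power, SAP 5 says: "The sample size was chosen to have 90% power". Its expected cases are "89 cases for Placebo and 27 cases for VLP in case of 4430 per group considering 10% dropout rate". Subjects "will be randomized in a 1:1 ratio into one of two parallel treatment groups". SAP 8.6.2.2 plans score limits for RR.

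**Input not in the documents.** The share of cases lost in each arm through early antiviral use, lp (placebo) and lv (vaccine). I assume a range of 0 to 30%.

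**Step 1: reproduce the plan.** Expected cases: 4430 × 0.02 = 88.6 and 4430 × 0.006 = 26.6, which agree with 89 and 27. Power was obtained by enumerating two independent binomials and summing the probability of outcomes that meet the criterion. SAP 5 does not name the interval used in its simulation, so two were tried:

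- Exact conditional limits: given the total number of cases, the vaccine count at the margin is binomial with probability 0.6/(0.6 + 1) = 0.375, and success needs a lower-tail probability of at most 0.025. Power is 0.9025 (4430 per group, 2%) and 0.8056 (4490 per group, 1.5%). These match the stated 90% and 80%.
- Score limits, as planned: 0.924 and 0.829.

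**Step 2: model the loss.** Remove lost cases from numerator and denominator:

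q0 = p0(1 − lp)/(1 − p0·lp), q1 = p1(1 − lv)/(1 − p1·lv), VE = 1 − q1/q0.

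Example, lp = 20% and lv = 10%: q0 = 0.016/0.996 = 0.01606; q1 = 0.0054/0.9994 = 0.00540; VE = 1 − 0.3363 = 66.4%. If the lost cases stay in the denominator as non-cases, VE = 1 − 0.3 × 0.9/0.8 = 66.25%, so that choice hardly matters.

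**Step 3: results (4430 per group, ARU 2%, true VE 70%).**

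| Lost share, placebo / vaccine | Cases lost | VE | Power, exact | Power, score |
|---|---|---|---|---|
| 0 / 0 | 0 / 0 | 70.0% | 0.903 | 0.924 |
| 5% / 5% | 4.4 / 1.3 | 70.0% | 0.887 | 0.910 |
| 10% / 10% | 8.9 / 2.7 | 70.0% | 0.872 | 0.893 |
| 20% / 20% | 17.7 / 5.3 | 70.1% | 0.831 | 0.850 |
| 10% / 5% | 8.9 / 1.3 | 68.4% | 0.822 | 0.848 |
| 20% / 10% | 17.7 / 2.7 | 66.4% | 0.698 | 0.724 |
| 10% / 0 | 8.9 / 0 | 66.7% | 0.765 | 0.794 |
| 10% / 20% | 8.9 / 5.3 | 73.4% | 0.944 | 0.954 |

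Equal shares remove 88.6/26.6 = 3.3 placebo cases for each vaccine case and leave VE unchanged. VE falls when placebo loses the larger share and rises when vaccine does.

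**The case against.** Four points can be made in defence of the plan.

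- **Swabbing after an antiviral is not forbidden.** Where the protocol wants no swab (onset before Day 14) it says so outright. The antiviral sentence can be read as an order of events whose breach is a deviation, with the swab still due under Table 1 note 5. This stands: a reader might infer that a treated subject cannot be swabbed, but the text is ambiguous and does not say that.
- **Leaving PP is not automatic.** Only a major deviation counts, judged blind and under an impact test. This also stands. But it leaves the handling of RT-PCR-positive subjects to a case-by-case decision that could be settled in advance.
- **FAS helps.** It keeps every treated subject who was swabbed and positive. That is correct for the second route of loss; it cannot recover illnesses that were never swabbed.
- **The size is unanchored and probably limited.** The population is healthy and at relatively low risk, subjects are told to report within 24 hours, contact is at least three times a week, and antivirals are barred before the swab. The 2% attack rate is already for laboratory-confirmed, matched influenza, so taking off further unconfirmed cases may count some ascertainment loss twice. This stands, and it is why the table shows a range and not an estimate.

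**Conclusion.** The point holds as a conflict between passages with an avoidable loss of cases. The rules on swab order, prohibited medication and PP membership can together drop true influenza cases because of how the illness was treated.

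The firm consequence is loss of cases and power: with 10% lost in both arms, exact power goes from 0.903 to 0.872 (score: 0.924 to 0.893) and VE stays at 70%. These figures rest on the SAP's own design assumptions plus an assumed loss rate.

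Two stronger readings are not supported:

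- A reader might infer that VE is biased because more cases are lost from placebo. The larger count follows from VE above zero; bias needs a larger share lost in one arm. A downward bias is the more likely direction if early treatment follows severity and vaccination makes illness milder, but the documents state neither. On that reading the risk is a missed success, not a false one. The opposite imbalance would raise VE.
- A reader might infer that a positive RT-PCR after an antiviral is a lost primary case. It is laboratory-confirmed influenza, but a primary case only if typing shows a matched strain.

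**What to change.** Leave the antiviral restriction in Protocol 5.3 and criterion 17 as it is. Then:

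1. **Swab wording** (Protocol 10.2.1; SAP 8.6.1; Table 2 note 1 and the Figure 2 notes in both documents). Reconcile with Table 1 note 5: swabs are preferably taken before any antiviral, but are still taken within the same 36 hours of reporting if one has been started, and the antiviral start time is recorded.
2. **SAP 6.3 and 6.5.** State that antiviral use after illness onset and before the swab is not by itself a reason for exclusion from PP. It may still be logged as a deviation.
3. **Case definition in the SAP.** State that a positive RT-PCR on such a swab counts as laboratory-confirmed influenza. Primary-endpoint status follows from the usual strain-match typing, and un-typed cases count only in the any-strain endpoints.
4. **Reporting.** Tabulate by arm the illnesses treated before the swab and those not swabbed, so that a differential loss would be visible.

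The cost is a wording amendment to the protocol and SAP, one table, and a start time added to medication dates already collected. No new procedure is needed, since the swabs are already due. Some swabs taken after an antiviral may be RT-PCR-negative or un-typeable, which is no worse for case finding than having no swab.

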**AND**

- He/she has at least one of the following systemic symptoms:
  - Fever (defined as a temperature  $> 37.2^{\circ}\text{C}$  or  $> 99.0^{\circ}\text{F}$ );
  - Chills;
  - Tiredness;
  - Headache; or
  - Myalgia.

## **10.2.2 Efficacy Endpoints**

### **10.2.2.1 Primary Endpoint**

- Occurrences of protocol-defined respiratory illness due to laboratory-confirmed influenza ( $\geq 14$  days post-vaccination) caused by influenza viral types/subtypes that are matched (and/or antigenically similar) to the strains covered in the vaccine formulation.

### **10.2.2.2 Secondary Endpoints**

- Occurrences of protocol-defined respiratory illness due to laboratory-confirmed influenza ( $\geq 14$  days post-vaccination) caused by any influenza viral types/subtypes (matched, mismatched, and un-typed);
- Occurrences of laboratory-confirmed influenza (according to protocol defined ILI) illnesses ( $\geq 14$  days post-vaccination) caused by influenza viral types/subtypes that are matched (and/or antigenically similar) to the strains covered in the vaccine formulation;
- Occurrences of laboratory-confirmed influenza (according to protocol defined ILI) illnesses ( $\geq 14$  days post-vaccination) caused by any influenza viral types/subtypes (matched, mismatched, and un-typed);
- Occurrences of protocol-defined ILI  $\geq 14$  days post-vaccination (confirmed or not).

### **10.2.2.3 Exploratory Endpoints**

- Occurrences, per age stratum, of laboratory-confirmed influenza ( $\geq 14$  days post-vaccination) caused by influenza viral types/subtypes that are matched (and/or antigenically similar) to the strains covered in the vaccine formulations, according to protocol-defined respiratory illness;
- Occurrences of laboratory-confirmed influenza illnesses ( $\geq 14$  days post-vaccination) caused by mismatched influenza viral strains, according to protocol-defined respiratory illness;

- Occurrences of respiratory illness  $\geq$  14 days post-vaccination (confirmed or not).

